#### 13.3.2 Urine Sampling for Drug-related Renal Injury Exploratory Biomarkers

Urine samples for drug-related renal injury exploratory biomarkers will be collected according to the time schedule presented in Appendix 2.

Samples will be taken as an aliquot from PK urine collection after the sample has been weighed. Urine samples will be collected and processed as detailed in the Clinical Sample Processing Manual.

Samples will be stored and may be analysed at the end of the trial retrospectively or as required during the study if medically relevant changes in the renal parameters of safety laboratory assessments are observed (ie, BUN, creatinine):

- α-GST
- CLU
- CysC
- KIM-1
- NGAL

- OPN
- ALB
- TPRO

The samples will be stored until finalisation of the clinical study report, and destroyed if no analyses are to be performed.

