#### 7.1.3 Exploratory Objectives

- To investigate any potential changes to renal toxicity markers in plasma and urine.
- To investigate the metabolite profile of DNDI-0690.
- To assess the effect of DNDI-0690 on Holter ECG parameters.
- To investigate the PK of DNDI-0690 after singles doses in the fed versus fasted state in healthy male subjects
- To investigate the PK of DNDI-0690 after single doses in healthy WONCBP versus healthy male subjects

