#### 7.2.3 Exploratory Endpoints

- Changes in clinical early renal toxicity markers in urine: alpha-glutathione Stransferase (α-GST), clusterin (CLU), Cystatin C (CysC), Kidney Injury Molecule-1 (KIM-1), neutrophil gelatinase-associated lipocalin (NGAL), osteopontin (OPN), albumin (ALB) and total protein (TPRO).
- Identification of DNDI-0690 metabolite profile (to be reported separately)
- Analysis of Holter extracted ECGs for the following parameters: RR, heart rate (HR), PR, QRS, QT, corrected QT interval by Fridericia's formula (QTcF), corrected QT interval by Bazett's formula (QTcB), ΔHR, ΔRR, ΔPR, ΔQRS, ΔQT, ΔQTcF and ΔQTcB.
- Comparison of the PK parameters AUC(0-t), AUC(0-inf) and Cmax of DNDI-0690 in the fed state versus fasted state in male subjects
- Comparison of the PK parameters AUC(0-t), AUC(0-inf) and Cmax of DNDI-0690 in WONCBP subjects versus male subjects

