- Criteria to be used to define each of the analysis populations
- Additional detail covering the analyses and/or description of primary and secondary analyses and safety data
- Handling of missing data, unused or spurious data

- Handling of data from withdrawn subjects
- Unblinding procedures and maintaining the blind

Any deviations from the originally planned analysis as per the RAP will be documented in the clinical study report.

All safety (including safety ECGs parameters) and PK data will be listed.

All safety ECG parameters (see Section 13.3.1 for parameters) and their changes from baseline will be summarised by dose regimen and time point.

As described in Section 13.3, all Holter extracted ECGs and urinary biomarker data, will not be analysed as part of this study at this stage.

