Haematology, coagulation and clinical chemistry, LDH, BUN, Uric acid, GLDH, Cholesterol and Cystatin C at each time point. Virology at screening only. Creatinine clearance will be estimated at screening for eligibility purposes and at each time point, from serum creatinine using the Cockcroft-Gault equation.

h Time points may be altered based on emerging data from previous cohorts, see Section 8.2.1.

Post-menopausal female subjects only

 Holter monitoring will begin at least 1 h prior to dosing and end 24 h post-dose after last PK time point. All ECG extractions will be taken in triplicate. Three sets of triplicate ECG extractions to be taken at pre-dose (for baseline). Holter extraction time points on Day 1 will be: pre-dose and 0.5, 1, 1.5, 2, 2.5, 3, 4, 6, 9, 12 and 24 h post-dose.

k ECGs to be taken in triplicate at pre-dose (for baseline), all post-dose time points single ECG. An ECG can be repeated for any reason (technical in particular). The Principal Investigator or sub-investigator must double-check the results.

Blood pressure and HR at every time point. Tympanic temperature at screening and pre-dose only.

m Urine will be collected for DNDI-0690 at the following intervals: Pre-dose, 0-12, 12-24, 24-48, 48–72 h post-dose. See Section 13.1.2 for more details.

n Urine samples for exploratory biomarkers for drug-related injury will be taken as an aliquot from PK urine collection at Pre-dose, 12, 24, 48 and 72 h post-dose. See Section 13.3.2 for details.

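### The exploratory objective and endpoint on early renal markers are unconditional, but the plan guarantees no urine result, destroys unassayed samples and ties no endpoint to the plasma half

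*Protocol*

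**What the plan says.** **Objective and endpoint.** Protocol 7.1.3, repeated in the Synopsis, has the exploratory objective "To investigate any potential changes to renal toxicity markers in plasma and urine". The matching endpoint in 7.2.3 is "Changes in clinical early renal toxicity markers in urine", followed by eight markers: alpha-GST, clusterin, cystatin C, KIM-1, NGAL, osteopontin, albumin and total protein. Neither carries a condition, and the endpoint names no plasma or serum marker.

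**Whether the assays are run.** Section 6.4 says early renal markers in plasma and urine may be looked at if renal function changes. Section 13.3.2 says: "Samples will be stored and may be analysed at the end of the trial retrospectively or as required during the study", and continues "if medically relevant changes in the renal parameters of safety laboratory assessments are observed (ie, BUN, creatinine"). Section 15.4 says "all Holter extracted ECGs and urinary biomarker data, will not be analysed as part of this study at this stage".

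**What happens to the samples.** Section 13.3.2: "The samples will be stored until finalisation of the clinical study report, and destroyed if no analyses are to be performed".

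**Blood markers that are measured.** Appendix 1 lists serum cystatin C among the safety tests, and the safety laboratory footnote in Appendix 2 includes "LDH, BUN, Uric acid, GLDH, Cholesterol and Cystatin C at each time point". The primary endpoint in 7.2.1 covers safety laboratory parameters, with a focus on serum creatinine, BUN and CLcr.

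**The concern.** An objective stated without condition should lead to a planned result. Here it leads to samples that may or may not be assayed, a statistics section that says they will not be analysed for now, and destruction if no assay is planned. A later analysis plan can settle how marker data are summarised, but it cannot bring back destroyed urine.

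The in-study prompt also fits the purpose poorly. The protocol calls these early markers, and their added value lies in subjects whose BUN and creatinine have not moved. Prompting the assay by a change in BUN or creatinine leaves exactly that situation to the optional retrospective run. No threshold defines a medically relevant change.

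The question is a real one for this compound. Section 5.3.1.3 identifies the kidney as a target organ in the cynomolgus monkey, and 6.4 mentions a possible class effect on the kidney.

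**Working it through.** No power, alpha or effect size is involved; 15.1 states that no formal sample size calculation was made. The check sets the sections side by side and counts samples.

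**1. Commitment on urine markers, section by section**

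| Section | Status of the urine markers |
|---|---|
| 7.1.3 | objective, no condition |
| 7.2.3 | endpoint, no condition |
| 6.4 | may be investigated, if renal function changes |
| 13.3.2 | optional at end of trial, or during the study on a BUN/creatinine change |
| 15.4 | not analysed as part of this study at this stage |

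These cannot all stand. Section 15.4 refers back to 13.3 as its source. Section 13.3.1 does defer the Holter analysis, but 13.3.2 only makes the urine assays optional. The reference therefore does not support the statement for urine.

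**2. Samples at stake**

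- Subjects: 8 cohorts x 8 = 64, which matches the Synopsis. With 2 replacements per cohort, 64 + 16 = 80, which matches 8.4.
- Aliquots per subject (Appendix 2): pre-dose, 12, 24, 48 and 72 h = 5.
- Scheduled aliquots: 64 x 5 = 320 (80 x 5 = 400 at the maximum).
- Assays that the text guarantees: 0.

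**3. Plasma half**

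- 7.1.3 names plasma; 7.2.3 lists urine only. The cystatin C in 7.2.3 is the urinary one.
- Appendix 2 schedules no plasma sample for exploratory renal markers.
- Serum cystatin C is taken with every safety laboratory panel: screening, Day -1, 24, 48 and 72 h, and follow-up. By design this covers 8 x 6 = 48 active and 8 x 2 = 16 placebo subjects.
- 15.4 summarises safety laboratory data by dose level, all active combined and all placebo combined, with changes from baseline as required. The data will therefore be reported, but no endpoint links them to the objective.

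**4. How often the prompt might occur**

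The protocol gives no rate. Let p be an assumed probability that an active subject shows a medically relevant BUN or creatinine change. The chance of at least one among 48 active subjects is 1 - (1 - p)^48:

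| Assumed p | Chance of at least one |
|---|---|
| 0.5% | 21% |
| 1% | 38% |
| 2% | 62% |
| 5% | 91% |
| 10% | 99% |

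The range is too wide to say whether an in-study assay is likely.

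**5. Comparison within the protocol**

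Section 13.3.1 archives the Holter recordings for up to 25 years, for analysis with the MAD trial if development continues. The renal samples have no such provision.

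**The case against.** The best defence is that storing first and deciding later is a legitimate choice for an exploratory objective in a single-dose study, where 6.4 calls the renal risk low. Renal safety is covered elsewhere: creatinine, BUN and CLcr are in the primary endpoint, and the escalation criteria in 8.2.1 use CLcr and creatinine. This stands. It limits the weight of the point and means that compulsory assays are a preference, not a correction. It does not explain why the objective and endpoint are worded as firm commitments, or why the samples must be destroyed at report finalisation.

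A reader might infer four stronger things that the protocol does not support:

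- *Serum cystatin C goes unused.* It is a safety laboratory test and falls under the summaries in 15.4 and the primary safety endpoint. What is missing is its link to this objective.
- *The prompt will probably never occur.* No rate is stated, and the assumed range above runs from 21% to 99%.
- *Only subjects with a creatinine change would be assayed, with no placebo reference.* Section 13.3.2 does not say whose samples would be run. Aliquots are scheduled for every subject, placebo included. A placebo comparison is not assured, but it is not excluded.
- *The end-of-trial run also needs a BUN or creatinine change.* In 13.3.2 the condition most naturally attaches to the in-study route. Section 6.4 does read as conditional, so this needs clarifying.

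Nor does any section plan to use these urine samples in the MAD trial. Keeping them would preserve an option, not a planned analysis.

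**Conclusion.** The point holds as an internal conflict with an irreversible step at its end. The objective and urine endpoint are firm in 7.1.3 and 7.2.3, conditional in 6.4, optional in 13.3.2 and set aside in 15.4. No result is guaranteed from 320 scheduled aliquots, and those not assayed are lost once the report is final. A change in an early marker without a BUN or creatinine change would be seen only through the optional retrospective run. The plasma half has relevant data in serum cystatin C but no endpoint tied to it.

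Severity is modest: the objective is exploratory, and neither renal safety monitoring nor dose escalation depends on these markers. The conclusion rests on the protocol text and on planned enrolment of 64. It needs no assumption about how often BUN or creatinine will change.

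**What to change.** 1. **7.2.3:** name serum cystatin C, change from Day -1 by dose level and pooled placebo, as the blood renal-marker endpoint. The data are already collected, so the cost is wording and at most one table.
2. **13.3.2:** replace destruction at report finalisation with retention until the MAD decision, as 13.3.1 does in principle for the Holter recordings. State that any end-of-trial run does not depend on a BUN or creatinine change and includes placebo subjects. The cost is freezer storage and consent wording that covers it.
3. **6.4, 7.1.3, 7.2.3, 13.3.2 and 15.4:** make them agree. If the urine markers are not to be assayed, say that the urine objective is conditional and that this trial draws no conclusion on early urinary renal markers. The cost is wording only.
4. **Before any assay:** the aliquots come from the PK urine collection, whose containers hold bovine serum albumin (13.1.2). Check that this does not invalidate total protein and, depending on assay specificity, albumin.

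Assaying all or some of the stored samples is optional; items 1 to 3 do not require it.

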# 14 Assessment of Safety

## 14.1 Safety Definitions

# 14.1.1 Adverse Events

An AE is any untoward medical occurrence in a clinical trial subject where a medicinal product has been administered, which does not necessarily have a causal relationship with this treatment. For this study, the untoward medical occurrences that may occur in a subject before receiving study medication are referred to as a "pre-dose AE" or once a medicinal product has been administered, as an TEAE and should be collected within the database.

It can therefore be any unfavourable and unintended sign (eg an abnormal laboratory finding), symptom, or disease temporally associated with the use of a medicinal product, whether or not considered related to the medicinal product.

Definition of an AE includes worsening (in severity and frequency) of pre-existing conditions ("Medical history") before first IMP administration and abnormalities of procedures (ie. ECG ...) or laboratory results which are assessed as "clinically significant".

#### 14.1.2 Clinically Significant Laboratory Procedures/Abnormalities

For every laboratory assessment, the investigator will evaluate if the laboratory test is normal or abnormal. If abnormal (after repeat test as required), the investigator will assess if this finding is clinically significant or not. If a laboratory parameter is abnormal and clinically significant, it should be reported as an AE.

An abnormal laboratory/procedure result must be compared with the previous value taking into account normal values in the studied population/country.

A TEAE is a new fact after the administration of the first dose of the study drug or a worsening in the condition; in the case of abnormal laboratory/procedure tests results, it is an increase in severity (clinical intensity) of the abnormality which is judged clinically significant by the investigator.

Laboratory/procedures (ie. ECG...) abnormalities should be assessed as "clinically significant" (and therefore have to be reported as an AE) if they meet at least one of the following conditions:

- The abnormality suggests a disease and/or organ toxicity AND this abnormality was not present at the screening visit or is assessed as having evolved since the screening visit;
- The abnormality requires medical intervention or concomitant therapy;
- Furthermore, laboratory abnormalities associated with clinical signs and symptoms will also be considered clinically significant.

When reporting an abnormal laboratory result as an AE, a clinical diagnosis should be recorded rather than the abnormal value itself, if available. However, in these cases, the AE should be recorded as the syndromic clinical diagnosis (eg, acute pancreatitis instead of each finding separately: high levels of amylase, high levels of lipase, abdominal pain and vomiting; eg "hypokalaemia" rather than "decreased potassium levels").

# 14.1.3 Adverse Drug Reaction

An adverse drug reaction (ADR) is any AE where a causal relationship with the IMP is at least a reasonable possibility (possibly related, probably related or definitely related). This means that there are facts (evidence) or arguments to suggest a causal relationship between the event and the IMP (see definition of causality below).

# 14.1.4 Serious Adverse Events

An SAE is defined as any untoward medical occurrence that at any dose:

- results in death
- is life-threatening (at the time of the event): in this context refers to an AE in which the patient was at risk of death at the time of the AE; it does not refer to an AE that hypothetically might have caused death if more severe;
- requires hospitalization or prolongation of existing hospitalization: ie. the AE requires at least an overnight admission or prolongs a hospitalisation beyond the expected length of stay;
- results in persistent or significant disability or incapacity: ie. the AE resulted in a substantial disruption of the subject's ability to conduct normal activities;
- consists of a congenital anomaly or birth defect: ie. an AE outcome in a child or foetus
  of a subject exposed to the IMP before conception or during pregnancy;
- an important medical event as recognised by the PI: ie, AE is medically significant: medical and scientific judgment should be exercised in deciding whether other situations should be considered serious events/reactions, such as important medical event that may not be immediately life-threatening or results in death or hospitalization but may jeopardize the subject or may require intervention to prevent one of the other outcomes listed in the above definition should also usually be considered as serious.
- In addition, any suspected transmission via a medicinal product of an infectious agent is also considered a serious adverse event/reaction.

#### 14.1.5 Unexpected Adverse Reaction

An unexpected adverse reaction is an adverse reaction, whose nature, severity or outcome is not consistent with the applicable product safety reference information on the IMP ie. the IB.

#### 14.1.6 Suspected Unexpected Serious Adverse Reactions (SUSARs)

SUSARs are SAEs which are believed to be related to an IMP and are both unexpected (ie the nature or severity is not expected from the information provided in the IB) and serious. SUSARs are subject to expedited reporting to the MHRA, EMA and EC (see Section 16.3.2 for details on reporting SUSARs).

#### 14.2 Reference Documents for Expectedness Assessment

The reference document for expectedness assessment of SAE related to study product for the present study is the IB currently in force at the time of SAE occurrence.

# 14.3 Recording Adverse Events

AEs will be recorded from the time of providing written informed consent until discharge from the study at the follow-up visit.

During each study visit the subject will be questioned directly regarding the occurrence of any adverse medical event according to the schedule in the source. All AEs, whether ascribed to study procedures or not, will be documented immediately in the source. This will include the date and time of onset, a description of the AE, severity, duration, actions taken, outcome and an investigator's current opinion on the relationship between the study drug and the event. A diagnosis and final opinion on the relationship between the study drug and the event will be provided at the end of the study by the investigator.

Any subject who withdraws from the study due to an AE will be followed up until the outcome is determined and written reports provided by the investigator.

#### 14.4 Analysis of Events

#### 14.4.1 By the Investigator

Each AE is to be classified by the investigator (in this order):

- For severity
- For causality
- As serious or non-serious

#### 14.4.2 Grading of Adverse Event Severity

The Investigator will evaluate each event with regard to its severity. The severity of the AEs will be determined in the following manner:

Mild An AE that is easily tolerated by the subject, causes minimal discomfort and does not interfere with everyday activities Moderate An AE that is sufficiently discomforting to interfere with normal everyday activities; intervention may be needed An AE that prevents normal everyday activities; treatment or other Severe intervention usually needed Life-The subject is at significant risk of life; it does not refer to an event which hypothetically might have caused death if it were more severe Threatening (life-threatening consequences, urgent intervention required). Death related to an event. Death

When the severity of an AE changes over time, each change in severity will be recorded in the source documents until the event resolves. However, only one AE and the maximum severity will be recorded in the source for each separate event. If the AE resolves but then recurs, each will be recorded as a separate AE, with the appropriate start and stop times.

# 14.5 Assessment of Causality

For both serious and non-serious AEs, the investigator is required to assess the possible relationship between the AE and each study drug (ie. to determine whether there exists a reasonable possibility that the study drug caused or contributed to the AE).

This means that there are facts (evidence) or arguments to suggest a causal relationship.

To help investigators with the decision binary tree yes/no (ie. Related/Not related) in the evaluation of causality, the Council for International Organizations of Medical Sciences (CIOMS VI) group recommends that investigators be asked to consider the following before reaching a decision:

- Medical history (including presence of risk factors)
- Lack of efficacy/worsening of existing condition
- Study medications
- Other medications (concomitant or previous)
- Withdrawal of study medication, especially following trial discontinuation / end of study medication
- Erroneous treatment with study medication (or concomitant)
- Protocol related procedure

The terms for reporting are:

- **Definitely related**. The adverse event and administration of study agent are related in time, and a direct association can be demonstrated.
- **Probably related**. The adverse event and administration of study agent are reasonably related in time, and the adverse event is more likely explained by study agent than other causes.
- **Possibly related**. The adverse event and administration of study agent are reasonably related in time, and the adverse event can be explained equally well by causes other than study agent.
- **Probably not related.** A potential relationship between study agent and the adverse event could exist (ie. the possibility cannot be excluded), but the adverse event is most likely explained by causes other than the study agent.
- **Not related**. The adverse event is clearly explained by another cause not related to the study agent.

Note: When compared to Binary "regulatory" classification, "not related" corresponds to "not related, probably not related" and "related" corresponds to "possible, probable and definitely related".

#### 14.5.1.1 Adverse Event Seriousness Assessment

The Investigator will evaluate the seriousness of any event.

#### 14.5.2 By the Sponsor

The Investigator is responsible for assessing seriousness and relatedness of an AE. In parallel, the Sponsor will also evaluate the seriousness of all events which are reported to him by the Investigator, and the causality of the study drug for each AE. The Investigator's decision will be independent of the Sponsor's.

AEs for which the Investigator consider that a causal link with the study product is a reasonable possibility will be considered to be suspected adverse effects. Should the evaluations of the Sponsor and the Investigator differ with regard to causality and the event being serious, then both will be reported in the declaration of suspected adverse reactions.

The Sponsor is responsible for determining the expectedness of the SAE, using the IMP reference safety information. Each SAE has to be classified by the sponsor as expected or unexpected for the IMP.

